
a. Study Design This is a 2-arm randomized controlled trial of 8 weeks of intervention involving 8 sessions of standardized exercise program and either concomitant iCBT and educational sessions or educational sessions only. Measurements will be taken at baseline and 8 weeks immediately following the intervention. The study will be conducted in National Bank of Bahrain Health Center (NBB HC).
 
b. Participants Participants will be recruited from NBB HC patients who will be referred to the physiotherapy department for knee pain. Health centers physicians will be informed about the study so that they can advise or refer eligible participants. Furthermore, the I-Seha database in the ministry of health will be searched for eligible participants who were diagnosed previously with one of the following diagnoses: osteoarthritis/ pain in joint/ pain in limb/ disorder of patella.
 
 • Inclusion criteria: 
 1. Age \geq 45 years 2. Depression level of at least 2 out of 6 on the Patient Health Questionnaire (PHQ-2) 3. Psychological distress level (K-6) of at least 7 out of 24 4. Knee pain for more than 3 months and for most days of the previous month 5. A minimum average knee pain intensity of 4 on an 11-point numeric rating scale in the previous week 6. Mild to moderate difficulty with physical activities on Knee Injury and Osteoarthritis Outcome Score Physical Function Short Form (KOOS-PS) 7. Has a smartphone with internet access. 
Determination of the depression and psychological distress levels were based on the mean levels of each variable in the high health care utilizer's group from Lentz et al. (2019) study. These two specific variables were chosen as these were improved after CBT interventions

--

(Bennell, Ahamed, et al., 2016; Lentz et al., 2019).

- **Exclusion criteria:**

1. Knee surgery including arthroscopy within the past 6 months
2. Awaiting or planning any back or lower limb surgery within the next 12 months
3. Current or past (within 3 months) oral or intra-articular corticosteroid use
4. Current long-term use of analgesics or drugs that cause analgesic effects such as the drugs used for epilepsy and bipolar disorders
5. Systemic arthritic conditions such as rheumatoid arthritis
6. Physiotherapy, chiropractic or acupuncture treatment or exercises specifically for the knee within the past 6 months

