7. Walking >30 min continuously daily or participating in a regular (more than twice a week) exercise program
8. Past participation in a CBT program
9. Inability to walk unaided as this is necessary for some of the physical testings
10. Grade IV on Kellgren and Lawrence grading system for Osteoarthritis classification
11. Medical condition precluding safe exercise such as uncontrolled hypertension or heart condition
12. Major joint pain (e.g. back, hip or ankle) to a greater extent than the knee pain that could limit the ability to exercise
13. Self-reported psychiatric history such as schizophrenia, epilepsy and bipolar disorders
14. Self-reported diagnosis of current clinical depression
15. Neurological condition such as Parkinson's disease, Multiple sclerosis or stroke
16. Inadequate written and spoken Arabic
17. Unable to comply with the protocol such as the inability to attend therapy sessions or attend assessment appointments at the health center.

- **Sample Size**

Convenient sampling has been used for this study based on the time and resources limit for this study. A number of twenty participants were assigned in each group.

c. Study Procedure

Eligible patients will be randomly allocated to either the study group or the control group (1:1). Initial assessments by self-reported questionnaires will be done at baseline. Initial assessment of knee joint will be done as well as the objective outcome measures that include: Isometric muscle strength of quadriceps using a hand-held dynamometer, functional tests (40mFPWT/ 30s CST/ 9 SST). The total time for completion of the three tasks will be approximately 25 min (Rejeski et al., 1995). Then the participant will be prescribed strengthening exercises under the supervision of the researcher and to follow at home, 3-4 times per week. Depending on the participant's allocation, the participant will be provided with a link to access online material of pre-recorded sessions of CBT or educational material about knee pain, healthy diet and other general information. In addition to their access to iCBT sessions, the study group will be able to access the same educational material that is accessed by the control group. On the 2nd -8th session, the physiotherapist will follow up on the exercises and progress as needed and will respond to any questions or doubts the participant has regarding the online sessions.

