- **Health-Related Quality of Life-Short Form-12 (SF-12)**

This is a questionnaire consisting of twelve questions that measure eight health domains to assess physical and mental health-related quality of life (Huo et al., 2018). The reliability and validity of this questionnaire are questionable, yet it will be used in this study as it was the only short form with free access that was found (Al Sayah et al., 2013). It will be administered through an online survey.

- **Maximum Isometric Muscle Strength**

Assessing quadriceps muscle strength can indicate the individual's mobility and pain and hence it will be assessed in this study (Luc-Harkey et al., 2018). Maximal voluntary isometric quadriceps muscle strength will be assessed using a hand-held dynamometer as described by Luc-Harkey et al (2018) (Figure 4). To do the test, a participant will be seated on an examination table with their knees flexed to 60° and their feet off the ground. The hand-held dynamometer will be positioned on the anterior aspect of the distal tibia, just superior to the malleoli. An inelastic strap will be secured around the treatment table under the participant and will be used to maintain the position of the hand-held dynamometer and the knee angle during each testing trial. The participant will grasp the examination table with his/her hands for stabilization, and the participant will be instructed to extend his/her knee "as hard as possible" into the hand-

held dynamometer. The participant will continue to exert force into the hand-held dynamometer for 4 s, and the maximum force across the trial will be recorded. Three testing trials will be completed, and the average force (Newtons [N]) across the three trials will be normalized to body mass (N/kg) (Luc-Harkey et al., 2018).

f. Data Collection

Data collection points will be done at 0 and 8 weeks. In addition to the outcome measures, descriptive data will be collected at baseline by an online questionnaire. Descriptive data to be collected are age, gender, employment status, marital status, body mass index (BMI), duration of knee symptoms, previous treatments, medical history, and medications.

g. Ethical Considerations

- Ethical Approval

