point. For continuous outcomes differences in mean change will be compared between groups using linear regression random effects modelling adjusted for baseline values of the outcome. Proportional odds models will compare improvement between groups based on perceived ratings of change as well as the proportion in each group who attain the minimum clinical important difference (MCID) for pain and function. The MCID to be detected in chronic musculoskeletal trials is a change in pain of 1 unit (out of 10) (Salaffi et al., 2004). The MCID to be detected in the 30sCST and 40mFPWT are 2.0 and 0.19 respectively (Dobson et al., 2013).

- **Limitations**

This study has limitations. First, the study will be conducted with one researcher which exposes it to a risk of bias, but this risk will be minimized by blinding participants to hypotheses. Second, the determined sample size might not be reached within the study's time frame and this might affect the effect size between both groups leading to no significant results between the group. Second, some of the Arabic translated questionnaires have low reliability and/ or low validity levels, thus limiting the generalizability of their results.

Expected outcomes:

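### No baseline covariate is named for the MCID responder comparison, although reaching an MCID generally depends on baseline: a minor gap that is free to close

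*Combined protocol and SAP*

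**What the plan says.** Two consecutive sentences in section h matter here. The first reads: "For continuous outcomes differences in mean change will be compared between groups using linear regression random effects modelling adjusted for baseline values of the outcome". The second assigns proportional odds models to perceived ratings of change and also to "as well as the proportion in each group who attain the minimum clinical important difference (MCID) for pain and function", and mentions no covariate. Section h then gives the thresholds: 1 unit on the 0-10 pain scale, 2.0 for the 30-second chair stand (30sCST) and 0.19 for the 40-m walk (40mFPWT).

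On the size of the trial, the Sample Size paragraph says: "A number of twenty participants were assigned in each group". Section c describes 1:1 random allocation and no stratification. Section h says that baseline scores will be inspected for comparability, but not what follows if the arms differ.

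**The concern.** Each threshold is a cut on the change between two visits. A patient who starts with more pain, slower walking or fewer stands usually has more room to improve and tends to regress towards the mean, so is more likely to be counted as a responder. If one arm starts worse by chance, its unadjusted responder proportion tends to be higher without any treatment effect.

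The continuous analysis corrects for this because baseline is in the model. If the responder analysis does not, the two analyses of the same primary outcome can disagree for a reason unrelated to iCBT. Leaving the covariate unstated also leaves the choice open until the baseline table has been seen.

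**Working it through.** **Inputs from the documents.** 20 per arm (Sample Size); 1:1 allocation (section c); two visits, "Data collection points will be done at 0 and 8 weeks" (section f); entry pain of at least 4 (section b); the three MCIDs (section h). There is no derived figure to reproduce, since the sample size rests on time and resources: "Convenient sampling has been used for this study based on the time and resources limit for this study".

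**Assumed inputs, not in the documents.** Bivariate normal scores; baseline to week-8 correlation ρ of 0.3-0.85; ratio r of week-8 SD to baseline SD of 1.0-1.5; responder rate p of 50-80%; no treatment effect.

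**Step 1. Size of a chance imbalance.** The SE of the difference in baseline means is SD × √(2/20) = 0.316 SD. A difference of at least that size arises in about a third of trials. One above 0.25 SD has probability 43%, and one above 0.5 SD 11%.

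**Step 2. Effect on the responder difference.** In baseline-SD units, the slope of change on baseline is b = ρr − 1, and SD(change) = √(b² + r²(1 − ρ²)). For an imbalance d, the size of the shift is

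Φ(z_p + |b|d / (2·SD(change))) − Φ(z_p − |b|d / (2·SD(change))),

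with its direction reversed when b is positive.

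Example: ρ = 0.5, r = 1, p = 50%. Then b = −0.5 and SD(change) = √(0.25 + 0.75) = 1. The term is 0.5 × 0.316 / 2 = 0.079, and Φ(0.079) − Φ(−0.079) = 0.063, or 6.3 points.

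Shift in percentage points for d = 0.316 SD, over p = 50-80%:

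| r | ρ = 0.3 | ρ = 0.5 | ρ = 0.7 | ρ = 0.85 |
|---|---|---|---|---|
| 1.0 | 5.2 to 7.5 | 4.4 to 6.3 | 3.4 to 4.9 | 2.4 to 3.5 |
| 1.25 | 4.1 to 5.9 | 2.9 to 4.1 | 1.2 to 1.7 | −1.2 to −0.8 |
| 1.5 | 3.2 to 4.5 | 1.7 to 2.4 | −0.6 to −0.4 | −4.1 to −2.9 |

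A separate null simulation with equal SDs at both visits gave about 2.5-7.5 points, and adjustment for baseline removed the shift.

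**Step 3. Check on whole-number pain scores.** Simulated baseline scores of 4-10 (SD 1.36), 20 per arm, 40,000 trials per scenario, responder = a drop of at least 1. One SE of imbalance is 0.43 units.

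| Week-8 SD | ρ | Responder rate | Shift (points) | SD of the responder difference, unadjusted → with the imbalance removed |
|---|---|---|---|---|
| 1.5 | 0.48 | 63% | 5.1 | 15.3 → 14.4 |
| 1.5 | 0.48 | 75% | 4.2 | 13.6 → 12.9 |
| 2.0 | 0.29 | 69% | 4.2 | 14.7 → 14.1 |
| 2.0 | 0.48 | 71% | 2.4 | 14.4 → 14.1 |
| 2.2 | 0.48 | 78% | 1.5 | 13.1 → 13.0 |
| 2.0 | 0.68 | 76% | −0.1 | 13.5 → 13.5 |

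The gain in SD is 0-6%; the largest is (15.3 − 14.4)/15.3 = 5.9%.

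**Step 4. Scale against sampling error.** The SE of the responder difference is √(2p(1 − p)/20): 15.8 points at p = 50% and 12.6 points at p = 80%.

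**Step 5. Type I error.** Null simulations on truncated whole-number pain scores (ρ 0.3-0.7, r 1-1.5, 60,000 trials per scenario) gave unconditional rates of 4.9-5.4% for a pooled z-test and 0.6-4.2% for a Wald test in unadjusted logistic regression.

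**The case against.** The strongest reply is that an unadjusted comparison of randomised arms is valid. The shift is part of the sampling variation that the confidence interval already covers, and Steps 4 and 5 bear this out. A reader might infer that the responder analysis is biased or has an inflated error rate; it does not. Rejection rates do rise in some scenarios among trials picked out for a large imbalance, but lower rates in the other trials offset this.

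A reader might also infer that the sponsor has chosen to leave baseline out. The text does not say so. It is silent on covariates for this model, and the inference rests only on the contrast with the sentence before.

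The size is not fixed by the documents either. The entry rule, "A minimum average knee pain intensity of 4 on an 11-point numeric rating scale in the previous week", narrows the baseline spread, so a larger week-8 SD is plausible, and that is where the shift shrinks or reverses. Nor should the unit be misread: an imbalance of one whole patient SD at 20 per arm is z = 1/0.316 = 3.16, with probability about 0.0016.

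Finally, it is tempting to call the proportional odds model wrong because it yields an odds ratio. On a two-level response it is ordinary logistic regression, which is a standard way to compare proportions. Preferring a difference in proportions is a reporting choice.

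What stands is that the covariate is unstated, that responder status generally depends on baseline, and that the two analyses of one outcome may be handled differently.

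**Conclusion.** The point holds as a minor gap in specification. If SDs are similar at both visits and the correlation is 0.3-0.7, a one-standard-error imbalance moves the unadjusted responder difference by roughly 2-7 points. If the week-8 SD is much larger and the correlation high, the movement is near zero and can reverse. All of this depends on assumed SDs, correlations and responder rates. The case for change is consistency with the continuous analysis and closing a choice that could otherwise be made after seeing the data. It is not the rescue of an invalid test.

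**What to change.** In section h, state that each MCID responder model (NRS, 30sCST, 40mFPWT) is a logistic regression with arm and the baseline value of the same outcome. Report the baseline-standardised difference in proportions with its 95% CI alongside the odds ratio. Keep the proportional odds model for the ordinal perceived ratings of change. If penalised estimation is wanted for sparse cells, specify it in advance for all of these models. A rule triggered only when an arm has 0 or 20 responders depends on the data and would miss an all-responder arm reduced by dropout.

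The cost is two or three sentences and a few lines of code. The baseline values are already collected, and no patients or visits are added. The downside is that little precision may be gained: about 0-6% in SD for pain, and possibly none.
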